9.2. Serum Pharmacokinetic Parameters

The following serum PK parameters will be calculated for adalimumab administered as CT-P17, US-licensed Humira, or EU-approved Humira by non-compartmental method using [REDACTED], with the following guidelines:

- Actual sampling times relative to dosing rather than nominal times will be used in the calculation of all derived PK parameters.
- There will be no imputation of missing data.

Parameter	Definition
Primary	
AUC _{0-inf}	Area under the serum concentration-time curve from time zero to infinity, calculated using the linear trapezoidal (linear interpolation) rule
AUC _{0-last}	Area under the serum concentration-time curve from time zero to the last quantifiable concentration, calculated using the linear trapezoidal (linear interpolation) rule
C _{max}	Maximum serum concentration
Secondary	
T _{max}	Time to C _{max}
t _{1/2}	Terminal elimination half-life, calculated as: $t_{1/2} = \ln 2 / \lambda_z$
λ _z	Terminal elimination rate constant estimated from the linear regression of the natural log-transformed concentration over time at the terminal phase. At least 3 time points (excluding C _{max}) and in general, adjusted correlation coefficient (r ²) greater than or equal to 0.85 is needed to calculate and retain λ _z and its associated parameters (t _{1/2} , AUC _{0-inf} , CL/F, and V _z /F). Values of adjusted r ² < 0.85 will be examined on a case-by-case basis for reliability to calculate and retain λ _z and its associated parameters. Pharmacokinetic parameters that do not meet this criterion will be listed but not summarized or included in the statistical analysis.
%AUC _{extrap}	percentage of the area extrapolated for calculation of area under the serum concentration-time curve from time zero to infinity. Percent extrapolation ≤ 20% will be required to retain AUC _{0-inf} and its associated parameters (λ _z , t _{1/2} , CL/F, and V _z /F). Pharmacokinetic parameters that do not meet this criterion will be listed but not summarized or included in the statistical analysis.
CL/F	Apparent total body clearance, calculated as: $CL/F = Dose/AUC_{0-inf}$
V _z /F	Apparent volume of distribution during the terminal phase after non-intravenous administration, calculated as: $V_z/F = (CL/F)/\lambda_z$

All PK analyses will be conducted by the [REDACTED]

[REDACTED].

Pharmacokinetic parameters will be presented in data listings and summarized in tables by treatment arm, using descriptive statistics (n, arithmetic mean, SD, %CV, geometric mean, minimum, median, and maximum). Additionally, primary PK parameters will be summarized by treatment and ADA status.

For AUC_{0-last} and AUC_{0-inf}, the results will be rounded to integer in listing presentations; summary statistics for minimum and maximum will be rounded to integer; arithmetic mean, median, and geometric mean will be rounded to 1 decimal place; SD and %CV will be rounded to 2 decimal places. For T_{max}, the results will be rounded to 2 decimal places in listing presentations; summary statistics for minimum and maximum will be rounded to 2 decimal places; arithmetic mean,

median, and geometric mean will be rounded to 3 decimal places; SD and %CV will be rounded to 4 decimal places. For all PK concentrations and other PK parameters, the results will be reported to 3 significant figures in listing presentations; summary statistics for minimum and maximum will be reported to 3 significant figures; arithmetic mean, median, and geometric mean will be reported to 4 significant figures; SD and %CV will be reported to 5 significant figures.

9.3. Statistical Analysis of Pharmacokinetic Data

The statistical analysis of the log-transformed primary endpoints ($AUC_{0-\text{inf}}$, $AUC_{0-\text{last}}$, and C_{\max}) will be based on an analysis of covariance model (ANCOVA) with treatment as a fixed effect and body weight as measured on baseline (Day -1), gender (male vs. female) and study center as covariates. The similarity of PK between; CT-P17 vs. US-licensed Humira, CT-P17 vs. EU-approved Humira, and US-licensed Humira vs. EU-approved Humira will be concluded if the 90% CIs for percent ratios of geometric LS means of each comparison are entirely contained within 80% to 125% for $AUC_{0-\text{inf}}$, $AUC_{0-\text{last}}$, and C_{\max} .

Statistical analysis will also be done by ADA status for both positive and negative subjects. If subjects for one of the ADA status category is missing or too small to conduct ANCOVA analysis, then the analysis will not be reported.

10. Safety and Immunogenicity Analyses

All safety and immunogenicity analyses will be based on the safety population unless otherwise stated.

10.1. Adverse Events

An AE is defined as any untoward medical occurrence associated with the use of a drug in humans, whether or not considered drug related. Subjects will be instructed to contact the investigator at any time after the ICF was signed if any symptoms develop.

All AEs will be collected from the date the ICF is signed and until the end of the subject's participation in the study, and will be coded by PT and SOC using MedDRA, Version 22.0 or higher. All AEs will be presented in a data listing for the safety population.

Relationship to study drug (unrelated, possible, probable, or definite) will be summarized and events will be considered to be related if relationship is possible, probable, or definite. Adverse events with no relationship or intensity will be summarized separately under a missing category.

Adverse drug reaction is defined as any treatment-emergent adverse event (TEAE) which has causal relationship with study drug at least a reasonable possibility, i.e., a TEAE which is considered as related.

All AEs will be graded for intensity according to the National Cancer Institute Common Terminology Criteria for Adverse Events (CTCAE) v5.0.

A TEAE is defined as any event not present before study drug administration or any event already present that worsens in intensity or frequency after study drug administration. Treatment-emergent AEs will be flagged in listings and all AE summaries will be restricted to TEAEs except the overall summary of AEs. All TEAE summary tables will include the number and percentage of subjects experiencing TEAEs by MedDRA SOC and PT, relationship, and intensity, by treatment arm and overall, and the total number of events overall, unless otherwise specified. Additionally, TEAEs, TESAEs, and TEAEs leading to study discontinuation will be summarized by treatment group, SOC, PT and intensity, regardless of relationship, displaying the number and percentage of subjects experiencing at least one TEAE. Summaries that are displayed by SOC and PT will be ordered by alphabetical order of SOC and PT. A subject with 2 or more TEAEs within the same SOC, PT, and relationship will be counted only once using the most severe intensity recorded in that level. Percentages will be based on the number of subjects in the safety population who received each treatment arm and overall.

For the purpose of inclusion in TEAE tables, the eCRF question “Did this AE start before administration of study drug?” on “Adverse Events” page will be used to determine TEAEs if the AE onset date is incomplete. If the answer is not available, incomplete AE onset and end dates will be imputed as follows:

- If the stop date of an AE is partial or missing, the following rules will be applied:
 - Missing day (e.g., XXFEB2019): Assume the last day of the month (e.g., 28FEB2019).
 - Missing day and month (e.g., XXXXX2019): Assume December 31st (e.g., 31DEC2019).
 - Missing day, month, and year (e.g., XXXXXXXX): Leave it as Missing.
- If the start date of an AE is partial or missing, the following rules will be applied. If the stop date of the AE is partial, imputed stop date will be used instead of reported stop date:
 - If the day of an AE is missing (e.g., XXFEB2019), the month and year of the partial date will be compared to the date of the study drug administration.
 - If the month and year are equal for both dates, the AE start date will be imputed as the earlier date of: (i) the date of the study drug administration, and (ii) the end date of the AE.
 - If the month and year are not equal, the AE start date will be imputed as the first day of the month (e.g., 01FEB2019).
 - If the day and month are missing (e.g., XXXXX2019), the year of the partial date will be compared to the date of the study drug administration.
 - If the years of both dates are equal, start date will be imputed as the earlier date of: (i) the date of the study drug administration, and (ii) the end date of the AE.
 - If the year is not equal, start date will be imputed as the 1st of January of the partial date year (e.g., 01JAN2019).

- If the AE start date is missing (e.g., XXXXXXXXXX), start date will be imputed as the earlier date of: (i) the date of the study drug administration, and (ii) the end date of the AE.

Relative start day or end day with respect to the dose date of study drug will not be calculated if the event start date or end date is incomplete.

The duration of the AE will be calculated using the below formula.

- For events with start time and end time collected: duration = adverse event stop datetime – adverse event start datetime
 - Present in minutes if duration is less than (<) 1 hour (60 minutes)
 - Present in hours with 1 decimal place if the duration is more than or equal to (\geq) 1 hour (60 minutes) but less than (<) 24 hours (1440 minutes)
 - Present in days with 2 decimal places if duration is more than or equal to (\geq) 24 hours (1440 minutes)
- For events without start time or end time collected: duration in days = adverse event stop date – adverse event start date + 1

All AEs recorded will be presented in a data listing for the safety population.

10.1.1. Incidence of Adverse Events

A summary table of overall AEs will be presented by treatment arm and overall for the safety population, including total number of AEs, total number of SAEs, total number of TEAEs, number and percentage of subjects with at least one AE, with at least one SAE, with at least one TEAE, with at least one treatment-emergent SAE (TESAE), with at least one TEAE leading to study discontinuation, with at least one TEAE leading to death, with at least one TEAE of hypersensitivity/allergic reaction, with at least one TEAE of ISR, with at least one TEAE of infection, and with at least one TEAE of malignancy.

10.1.2. Serious Adverse Events and Deaths

A SAE is defined as any untoward medical occurrence that at any dose meets any of the following outcomes:

- Results in death
- Is immediately life-threatening
- Requires in-patient hospitalization or prolongation of existing hospitalization
- Results in persistent or significant disability/incapacity
- Is a congenital anomaly/birth defect

Important medical events that may not result in death, be life threatening, or require hospitalization may be considered SAEs when, based upon appropriate medical judgment, they may jeopardize

the subject or may require medical or surgical intervention to prevent one of the outcomes listed in this definition. Examples of such medical events include allergic bronchospasm requiring intensive treatment in an emergency room or at home, blood dyscrasias or convulsions that do not result in in-patient hospitalization, or the development of drug dependency or drug abuse.

Unless otherwise specified, treatment-emergent SAEs will be summarized by treatment arm, overall and by relationship, intensity, SOC and PT displaying the number and percentage of subjects with at least one TESAE using only the most severe intensity recorded at each level of summarization. The total number of TESAEs will also be displayed.

All SAEs, including deaths, will be presented in a data listing for the safety population. All subjects who have a SAE with serious criteria of “death” will be presented in a data listing for the safety population.

10.1.3. Treatment-Emergent Adverse Events Leading to Study Discontinuation

The AE leading to study discontinuation will be determined based on question “Did the adverse event cause the subject to be discontinued from the study?” on “Adverse Events” page of eCRF. Unless otherwise specified, the TEAEs leading to study discontinuation will be summarized by treatment arm, overall and by relationship, intensity, SOC and PT displaying the number and percentage of subjects with at least one TEAE leading to study discontinuation. The total number of TEAEs leading to study discontinuation will also be displayed.

All AEs that lead to study discontinuation will be presented in a data listing for the safety population.

10.1.4. Treatment-Emergent Adverse Events of Special Interest

Treatment-emergent AEs of special interest (hypersensitivity/allergic reactions, ISRs, infections, and malignancy) will be determined as follows:

- **Hypersensitivity/allergic reactions:** Treatment-emergent AEs classified as hypersensitivity/allergic reactions are determined if the eCRF question “Is Adverse event classified as a Hypersensitivity/Allergic Reactions?” is answered as “Yes”. Signs and symptoms of hypersensitivity/allergic reactions will be captured on separate eCRF pages. Signs and symptoms of hypersensitivity/allergic reactions will be coded using MedDRA Version 22.0 or higher.
- **Injection site reactions:** Treatment-emergent AEs classified as ISRs are determined if the eCRF question “Is Adverse event classified as an injection site reaction (ISR)?” is answered as “Yes”. Signs and symptoms of ISRs will be captured on separate eCRF pages. Signs and symptoms of ISRs will be coded using MedDRA Version 22.0 or higher.
- **Infection:** Treatment-emergent AEs classified as infections are determined by SOC if the SOC is “Infections and Infestations”.
- **Malignancy:** Treatment-emergent AEs classified as malignancy are determined by SOC if the SOC is “Neoplasms benign, malignant and unspecified (incl cysts and polyps)”, excluding

events where any of the High Level Group Term, High Level Term, PT, and Lowest Level Term contains “benign”. And it will be determined to be included by medical review.

The TEAEs which are classified as hypersensitivity/allergic reaction, ISR, infection, and malignancy will be summarized by treatment arm, overall and by relationship, intensity, SOC and PT in separate tables. The total number of events and number of subjects with at least one TEAE classified as hypersensitivity/allergic reaction, or with at least one TEAE classified as ISR, or with at least one TEAE classified as infection, or with at least one TEAE classified as malignancy will also be displayed in corresponding table.

Signs and symptoms of hypersensitivity/allergic reactions and ISRs are summarized by SOC, PT, treatment arms and overall, and intensity for the safety population, respectively.

All TEAEs classified as hypersensitivity/allergic reactions, ISRs, infection, and malignancy will be presented in separate data listings for the safety population.

10.2. Clinical Laboratory Evaluations

Blood and urine samples will be performed by the local laboratory. All laboratory test results will be presented in the International System of Units (SI units). If the local unit provided by the laboratory is not consistent with the SI unit, the local unit will be converted to the SI unit. The conversion factors will be provided to CELLTRION, Inc. for review and approval before the DRM.

The following clinical laboratory assessments will be performed:

Hematology: Hematocrit, hemoglobin, red blood cell (RBC) count, white blood cell (WBC) count with differential, absolute neutrophil count, platelets

Serum Chemistry: Albumin, alkaline phosphatase (ALP), alanine aminotransferase (ALT), Aspartate aminotransferase (AST), blood urea nitrogen (BUN), calcium, chloride, total cholesterol, creatine phosphokinase (CPK), creatinine, creatine kinase-myocardial band isoenzyme (CK-MB), creatinine clearance (CrCl) [estimated by Modification of Diet in Renal Disease formula]^[1], C-reactive protein (CRP), gamma glutamyl transferase (GGT), glucose, lactate dehydrogenase (LDH), magnesium, potassium, sodium, total bilirubin, total protein, uric acid, direct bilirubin, triglycerides, inorganic phosphorus, high-density lipoprotein (HDL) cholesterol, Troponin I

Urinalysis: Color, pH, specific gravity, ketones, protein, glucose, bilirubin, nitrite, urobilinogen, occult blood, and microscopic examination^[2]

[1] Creatinine clearance (CrCl) will be calculated using serum creatinine level only at Screening and recorded on source document and eCRF

[2] Only the parameters including squamous cells, white and red blood cell will be presented in the listings.

Clinical laboratory testing (hematology, serum chemistry, and urinalysis) will be performed at Screening, on Day -1, and on Days 3, 8, 15, 29, 43, and 57, and at EOS.

Only the parameters specified in the protocol will be included in summary tables by laboratory categories: hematology, serum chemistry, and urinalysis. All parameters collected from the

laboratory will be included in the raw data and Study Data Tabulation Model, but only protocol-specified laboratory parameters and Troponin T (if it's performed) will be presented in the listings.

Abnormal clinical laboratory values will be flagged as either high or low or abnormal based on the reference ranges provided by the local laboratories for each laboratory parameter. The investigator will determine whether any of the abnormal clinical laboratory values are clinically significant or not clinically significant.

Clinical laboratory test results will be labeled with a CTCAE term, and grading will be applied to post-baseline values for numeric parameters based on CTCAE v5.0 where applicable. Grades which are part numeric and part clinical input will be assigned based on the numeric portion only; lower grade will be used if different grades share the same criteria. The criteria are listed in [Appendix 14.2](#). Unit conversion will be performed if the clinical laboratory unit is not consistent with unit in CTCAE v5.0, however it will be the CTCAE criteria unit that is converted as all laboratory findings will be reported in the SI units.

Actual values and changes from Baseline for quantitative clinical laboratory test results (hematology, serum chemistry, and urinalysis) will be summarized by treatment arm and overall at each time point using descriptive statistics (n, mean, SD, minimum, median, and maximum) for the safety population. Shift tables from baseline to each schedule post-baseline visit, will be generated for clinical laboratory test results (hematology, serum chemistry, and urinalysis) using normal; abnormal, clinically significant; abnormal, not clinically significant categories as appropriate, by treatment arm and overall for the safety population.

The number and percentage of subjects will be summarized by CTCAE term, CTCAE grade, and treatment arms and overall for the safety population, where this summary includes only the most severe case during the overall visits. The CTCAE terms and ranges for applicable parameters are listed in [Appendix 14.2](#). The CTCAE grades for this analysis will be Grade 1 (Mild), Grade 2 (Moderate), Grade 3 (Severe) and Grade 4 (Life-threatening). The CTCAE Grade 5 (Death) will not be applied in this analysis since death cannot be determined from a numeric laboratory result. If a subject's most severe result does not satisfy any CTCAE criteria, this subject will be summarized as "No Grade".

Absolute lymphocyte and absolute eosinophil will be calculated as follows:

- Absolute lymphocyte count ($10^9/L$) = [WBC ($10^9/L$) * Lymphocytes (Proportion of 1.0)].
- Absolute eosinophil count ($10^9/L$) = [WBC ($10^9/L$) * Eosinophil (Proportion of 1.0)].

Absolute lymphocyte count and absolute eosinophil count will be presented in the listing and summarized in the CTCAE grading table, but will not be included in the hematology summary tables.

Individual clinical laboratory test results will be presented in data listings for the safety population.

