Continuous variables will be summarized using descriptive statistics: number of subjects (n), mean, standard deviation (SD), minimum, median, and maximum, unless otherwise specified. For the summary statistics of all numerical variables unless otherwise specified, minimum and maximum will be presented to the same number of decimal places as the raw data, mean and median will be presented to one more decimal place than the raw data, and SD will be presented to two more decimal places than the raw data. If the geometric mean is to be presented, it will be set to the same precision as the mean. If the minimum value from the data is zero, then the geometric mean will not be calculated. Point estimates and confidence intervals (CIs) obtained from statistical procedures will be displayed to two decimal places.

For safety laboratory evaluations, for the purpose of summarization, any numeric values recorded below the lower limit or above the upper limit of quantification will be set to the respective limit for all related summaries. In listings, original results containing inequality sign will be displayed, unless otherwise specified.

Unless stated otherwise, all summary tables will present descriptive statistics and/or frequencies by treatment arms or overall (as appropriate), and all data listings will be sorted by treatment arm, subject number, and assessment date or visit date if applicable. In cases where more additional sorting is required, other variables will be included in the sort order as applicable.

Unless otherwise specified, all data collected on the eCRF will be presented in data listings by treatment arm and subject number where applicable.

If there are repeated measurements at a time point, the initial scheduled measurement at that time point will be used in the summary tables. If the initial scheduled measurement at that time point is missing, the next available repeated measurement will be used in the summary tables. The repeated measurements will be listed with indicator. Unscheduled visit results will not be included in the summaries except for determining baseline, but will be presented in data listings.

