5.2. Definition of Baseline

Unless stated otherwise, Baseline will be defined as the last non-missing measurement (including repeated and unscheduled assessments) before the administration of the study drug. Post-baseline will be considered as all measurements collected after the administration of the study drug.

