GGT increased	GGT	High	>ULN - 2.5 x ULN if baseline was normal; 2.0 - 2.5 x baseline if baseline was abnormal	>2.5 - 5.0 x ULN if baseline was normal; >2.5 - 5.0 x baseline if baseline was abnormal	>5.0 - 20.0 x ULN if baseline was normal; >5.0 - 20.0 x baseline if baseline was abnormal	>20.0 x ULN if baseline was normal; >20.0 x baseline if baseline was abnormal
Hemoglobin increased	Hemoglobin	High	Increase in >0 - 2 g/dL	Increase in >2 - 4 g/dL	Increase in >4 g/dL	-
Hyperkalemia	Potassium	High	>ULN - 5.5 mmol/L	>5.5 - 6.0 mmol/L	>6.0 - 7.0 mmol/L	>7.0 mmol/L
Hypermagnesemia	Magnesium	High	>ULN - 3.0 mg/dL; >ULN - 1.23 mmol/L		>3.0 - 8.0 mg/dL; >1.23 - 3.30 mmol/L	>8.0 mg/dL; >3.30 mmol/L
Hypernatremia	Sodium	High	>ULN - 150 mmol/L	>150 - 155 mmol/L	>155 - 160 mmol/L;	>160 mmol/L
Hypertriglyceridemia	Triglyceride	High	150 mg/dL - 300 mg/dL; 1.71 mmol/L - 3.42 mmol/L	>300 mg/dL - 500 mg/dL; >3.42 mmol/L - 5.7 mmol/L	>500 mg/dL - 1,000 mg/dL; >5.7 mmol/L - 11.4 mmol/L	>1,000 mg/dL; >11.4 mmol/L
Hyperuricemia	Uric acid	High	>ULN			
Hypoalbuminemia	Albumin	Low	<LLN - 3 g/dL; <LLN - 30 g/L	<3 - 2 g/dL; <30 - 20 g/L	<2 g/dL; <20 g/L	-
Hypoglycemia	Glucose	Low	<LLN - 55 mg/dL; <LLN - 3.0 mmol / L	< 55 - 40 mg/dL; < 3.0 - 2.2 mmol / L	< 40 - 30 mg/dL; < 2.2 - 1.7 mmol / L	<30 mg/dL; <1.7 mmol/L
Hypokalemia	Potassium	Low	<LLN - 3.0 mmol/L		<3.0 - 2.5 mmol/L	<2.5 mmol/L
Hypomagnesemia	Magnesium	Low	<LLN - 1.2 mg/dL; <LLN - 0.5 mmol/L	<1.2 - 0.9 mg/dL; <0.5 - 0.4 mmol/L	<0.9 - 0.7 mg/dL; <0.4 - 0.3 mmol/L	<0.7 mg/dL; <0.3 mmol/L

Hyponatremia	Sodium	Low	<LLN - 130 mmol/L	125-129 mmol/L	120-124 mmol/L regardless of symptoms	<120 mmol/L
Leukocytosis	Blood WBC	High			>100,000/mm ³	
Lymphocyte count decreased	Lymphocytes	Low	<LLN - 800/mm ³ ; <LLN - 0.8 x 10 ⁹ /L	<800 - 500/mm ³ ; <0.8 - 0.5 x 10 ⁹ /L	<500 - 200/mm ³ ; <0.5 - 0.2 x 10 ⁹ /L	<200/mm ³ ; <0.2 x 10 ⁹ /L
Lymphocyte count increased	Lymphocytes	High	-	>4,000/mm ³ - 20,000/mm ³	>20,000/mm ³	-
Neutrophil count decreased	Total Neutrophils	Low	<LLN - 1,500/mm ³ ; <LLN - 1.5 x 10 ⁹ /L	<1500 - 1,000/mm ³ ; <1.5 - 1.0 x 10 ⁹ /L	<1,000 - 500/mm ³ ; <1.0 - 0.5 x 10 ⁹ /L	<500/mm ³ ; <0.5 x 10 ⁹ /L
Platelet count decreased	Platelet count	Low	<LLN - 75,000/mm ³ ; <LLN - 75.0 x 10 ⁹ /L	<75,000 - 50,000/mm ³ ; <75.0 - 50.0 x 10 ⁹ /L	<50,000 - 25,000/mm ³ ; <50.0 - 25.0 x 10 ⁹ /L	<25,000/mm ³ ; <25.0 x 10 ⁹ /L

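### The CTCAE laboratory table ignores the pre-dose grade for 20 of 28 terms, so a stable baseline abnormality is tabulated as a post-dose grade

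*SAP*

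**What the plan says.** SAP 10.2 labels laboratory results with a CTCAE term and states that "grading will be applied to post-baseline values for numeric parameters based on CTCAE v5.0 where applicable". SAP 5.2 fixes the meaning of that term: "Post-baseline will be considered as all measurements collected after the administration of the study drug". Samples after dosing are taken "on Days 3, 8, 15, 29, 43, and 57, and at EOS", which makes seven scheduled post-dose visits. Subjects are then counted by term, grade and arm, and "this summary includes only the most severe case during the overall visits". SAP Section 5 (General Statistical Considerations) adds that "Unscheduled visit results will not be included in the summaries except for determining baseline", so the maximum runs over the seven scheduled draws.

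The limits are in SAP Appendix 14.2. Some rows refer to the subject's own baseline. Many do not; Grade 1 for triglycerides, for example, is simply "150 mg/dL - 300 mg/dL; 1.71 mmol/L - 3.42 mmol/L".

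SAP 10.2 also plans change-from-baseline summaries, and shift tables from baseline to each visit in three categories: normal, abnormal and clinically significant, abnormal and not clinically significant. It plans no shift table by CTCAE grade.

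**The concern.** A subject whose cholesterol or CPK is in the Grade 1 range before the injection and stays there is tabulated as a post-dose Grade 1. Nothing in the grade table separates that subject from one whose value became abnormal after dosing.

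Such subjects can be enrolled. Protocol 4.1 sets numerical laboratory limits only for C-reactive protein, ALT, AST and total bilirubin, and those limits allow up to 1.5 times the upper limit of normal (ULN). For other tests, Protocol 6.2.4 keeps out abnormalities judged clinically significant, and even these may enter with the sponsor's permission. Values that are out of range but judged not significant are admitted.

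Elsewhere the SAP takes the opposite approach. Under SAP 10.1 a pre-existing condition becomes a treatment-emergent event only if it is "any event already present that worsens in intensity or frequency after study drug administration". At stake is how the table can be read: its absolute frequencies, and the comparison of arms within the affected rows. Safety is part of the secondary objective.

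**Working it through.** The documents give no figure for this table, so there is none to reproduce. The check classifies the criteria and then gives a sense of scale under stated assumptions.

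**1. Classification of the 28 terms in SAP Appendix 14.2**

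| Use of baseline | Terms | Count |
|---|---|---|
| None | anemia, LDH, cholesterol, CPK, potassium high and low, magnesium high and low, sodium high and low, triglycerides, uric acid, albumin, glucose, leukocytosis, lymphocytes low and high, neutrophils, platelets, WBC low | 20 |
| Baseline or an increase | ALT, AST, ALP, GGT, total bilirubin, eosinophilia, hemoglobin increased | 7 |
| Mixed | creatinine (Grade 1 on ULN only; Grades 2–3 on multiples of baseline or of ULN) | 1 |

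The total is 20 + 7 + 1 = 28.

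**2. What an unchanged abnormal value does**

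- ALT, AST, ALP or GGT with an abnormal baseline: at least 1.5 or 2.0 times baseline is needed, so an unchanged value gets no grade.
- Bilirubin with an abnormal baseline, and eosinophilia: the value must exceed baseline, so an unchanged value gets no grade. For bilirubin any rise up to 1.5 times baseline is Grade 1.
- The 20 terms, and creatinine at Grade 1: the unchanged value is tabulated at its grade.

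**3. Persisting abnormalities alone**

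With 102 subjects per arm (SAP 5.1) and an assumed prevalence *b* of persisting baseline abnormality, 102 × *b* subjects are counted for that reason only. For *b* = 5%, 10% and 20% this is 5.1, 10.2 and 20.4 subjects. A count of worsened grades would include none of them.

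**4. Worst of seven, with no drug effect**

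Assume a one-sided limit exceeded by 2.5% of values at any single visit. If visits were independent, 1 − (1 − 0.025)^7 = 16.2% of subjects would be flagged. For correlated visits, a normal-theory simulation (one baseline and seven post-dose values, limit at 1.96 SD) gives:

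| Within-subject correlation (assumed) | Flagged | Already abnormal at baseline, of those flagged | Flagged per 102 | Of which normal at baseline |
|---|---|---|---|---|
| 0.5 | 11.4% | 13% | 11.7 | 10.2 |
| 0.7 | 8.9% | 21% | 9.1 | 7.2 |
| 0.9 | 5.7% | 40% | 5.9 | 3.5 |

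**5. An analyte that healthy adults may often exceed**

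For cholesterol, assume a mean of 170–185 mg/dL, between-subject SD of 30–35, within-subject CV of 6% and ULN of 200 mg/dL. None of these is in the documents. Simulation then flags 31–50% of an arm; 53–66% of those flagged were already above the limit at baseline. Counting only a rise over the baseline grade leaves 14–19%.

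**6. Effect on the comparison of arms**

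Let *p1* and *p2* be the proportions newly graded in two arms, and *b* the same persisting background in both. The table shows *b* + *p1* and *b* + *p2*. The difference stays *p1* − *p2*, but the ratio (*b* + *p1*)/(*b* + *p2*) moves towards 1, and each proportion is inflated by *b*.

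**The case against.** The strongest case against acting has four parts.

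- **Clinically important findings have another route.** Protocol 6.2.4 requires clinically significant post-dose abnormalities to be recorded as adverse events. SAP 10.1 grades these and counts only new or worsened ones, and the note to SAP Appendix 14.2 says the same of abnormal values with clinical input. This stands. What remains is largely asymptomatic, low-grade values.
- **Other outputs refer to baseline.** The shift tables show who was abnormal before dosing, and Grade 1 often lies just outside the normal range. This stands in part. The shift tables run visit by visit, with neither grades nor a worst-over-visits cell, so they cannot be used to correct the grade table. For absolute lymphocyte count SAP 10.2 excludes the hematology summary tables, which leaves the grade table as the only planned summary of that derived count.
- **The table is descriptive.** No test is planned, and 1:1:1 randomisation balances baseline abnormality in expectation. This stands and limits the consequence.
- **The remedy is partial.** Taking the worst of seven draws flags subjects by chance even after baseline is accounted for: 14–19% in the cholesterol example. This stands too.

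A reader might go further and infer that the whole table is affected, that it reports drug toxicity, or that the background could hide a real difference between arms. The documents support none of these. Seven terms already use baseline or an increase. The SAP calls the table neither a toxicity table nor treatment-emergent. A common background leaves the absolute difference unchanged, and no masking of a specific difference has been shown.

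**Conclusion.** The point holds for 20 of the 28 terms and for creatinine Grade 1. In those rows a stable pre-dose abnormality is presented as a post-dose grade, while an unchanged abnormal ALT, AST, ALP or GGT in the same table gets no grade. A reader cannot tell from the table which rows mean new or worsened.

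That much follows from the SAP text alone. The size does not: prevalence, correlation and the cholesterol distribution are all assumed, and limits come from local laboratories. The general case gives about 6–11% of subjects flagged, with 13–40% of those already abnormal at baseline. Both shares rise for analytes on which healthy subjects often exceed the limit.

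The consequence is overstated absolute frequencies and ratios pulled towards 1 in a descriptive safety table. The primary PK conclusion is unaffected. Severity: minor.

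**What to change.** In SAP 10.2, apply the Appendix 14.2 limits to the SAP 5.2 baseline value for every term without a baseline reference, and for creatinine Grade 1. Replace the single worst-grade count for these terms with a table of baseline grade by worst post-baseline grade, by arm. New or worsened grades can then be read separately from persisting ones. This is preferable to counting only worsened grades, which would remove persisting abnormalities from the summary. Keep all grades in the listing. State also the reference point for the hemoglobin-increased term, which Appendix 14.2 leaves open and which is presumably baseline.

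The cost is a few lines of SAP text, one derived variable and a somewhat larger table. Baseline samples are already scheduled at Screening and Day -1, so no new data are needed.
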